13.1.2 Definitions of response

12.1.2.1 Evaluation of response of target lesions

Complete response (CR): Disappearance of all target lesions. Any pathological lymph nodes (whether target or non-target) must have a reduction in short axis to < 10 mm.

Partial response (PR): At least a 30% decrease in the sum target lesions, taking as reference the baseline sum diameters.

Progressive disease (PD): At least a 20% increase in the sum target lesions, taking as reference the smallest sum on study recorded since the treatment started, or the appearance of one or more new lesions. In

addition to the relative increase of 20%, the sum must also demonstrate an absolute increase of at least 5 mm.

Stable disease (SD): Neither sufficient shrinkage to qualify for PR nor sufficient increase to qualify for PD, taking as reference the smallest sum diameters since the treatment started.

12.1.2.2 *Evaluation of response of non-target lesions*

Complete response: Disappearance of all non-target lesions and normalization of tumor marker level. All lymph nodes must be non-pathological in size (< 10 mm short axis).

Incomplete response/stable disease: Persistence of one or more non-target lesion(s) and/or maintenance of tumor marker level above the normal limits.

Progressive disease: Appearance of 1 or more new lesions and/or unequivocal progression of existing non-target lesion(s).

13.1.3 **Evaluation of overall response**

The best overall response is the best response recorded from the start of the treatment until disease progression/recurrence (taking as reference the smallest measurements recorded since the treatment started to determine response and progression).

Target lesions	Non-target lesions	New lesion	Overall response
CR	CR	No	CR
CR	Non-CR/Non-PD	No	PR
CR	Not evaluated	No	PR
PR	Non-PD or not all evaluated	No	PR
SD	Non-PD or not all evaluated	No	SD
Not all evaluated	Non-PD	No	NE
PD	Any	Yes or No	PD
Any	PD	Yes or No	PD
Any	Any	Yes	PD

Subjects with a global deterioration of health status requiring discontinuation of treatment without objective evidence of disease progression at that time should be classified as having "symptomatic deterioration". Every effort should be made to document the objective progression even after discontinuation of treatment.

In some circumstances, it may be difficult to distinguish residual disease from normal tissue. When the evaluation of complete response depends on this determination, it is recommended that the residual lesion be investigated (fine needle aspirate/biopsy) to confirm the complete response status.

13.1.4 **Definitions for response evaluations**

First documentation of response: The time between initiation of therapy and first documentation of PR or CR.

Duration of response: Duration of overall response - the period measured from the time that measurement criteria are met for complete or partial response (whichever status is recorded first) until the first date that recurrent or progressive disease is objectively documented, taking as reference the smallest measurements recorded since treatment started.

Duration of overall complete response: The period measured from the time that measurement criteria are met for complete response until the first date that recurrent disease is objectively documented.

Duration of stable disease: The period measured from the time that stable disease is documented until the first date that progressive disease is objectively documented.

Time to progression: A measurement from the study enrollment until the criteria for disease progression are met (or death occurs), taking as reference the smallest measurements recorded since the therapy started.

Overall survival: The overall survival time for each subject is the number of days from the day of first treatment to the earlier of (1) death (from any cause) or (2) the last date of subject contact. If the survival time does not correspond to the subject's death, then it is treated as censored.

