2.0 TRIAL DESIGN

This is a non-randomized Phase 2 trial using the Simon's optimal two-stage design. In the first stage, 13 eligible patients will enroll. If there are 2 or fewer patients with response (CR or PR), the study will be suspended for lack of sufficient efficacy. Otherwise, 16 additional patients will be accrued for a total of 29 patients. An accrual period of 24 months and follow-up period of 12 months are anticipated. More than 29 patients may be screened and/or enrolled depending on screen fails and dropouts before starting treatment.

Figure 2.1. Study schema

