4.0 STUDY ENDPOINTS

4.1 Primary endpoint

- Objective response (complete or partial response) per RECIST v1.1 (by blinded central review).

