- Discontinuation of pembrolizumab may be considered for participants who have attained a confirmed CR and have been treated for at least 8 cycles (at least 24 weeks), receiving at least 2 further cycles of cabozantinib and pembrolizumab beyond the date when the initial CR was declared.
- Completion of 2 years of therapy.
- Participant has any of the following non-overdose HECIs that are not reversible and manageable by therapy (see below). (Note: Temporary hepatic decompensation may occur in patients with cirrhosis exposed to TKIs.)
 - ALT >20 × ULN (confirmed within 1 week)
 - Drug-related total bilirubin >10 × ULN
 - CP score of > 8 points
 - Hepatic encephalopathy
 - Recurrence of a severe or life-threatening event, or of any of the laboratory abnormalities listed above, that are presumed to be immune-related
 - Uncontrolled ascites
- Subject is lost to follow-up.

Patients who come off study should be evaluated at 30 days (+ 7 days) after the last dose of cabozantinib or pembrolizumab (whichever is latest). AE assessment and reporting for patients who discontinue study treatment are described in Section 16.3.2. Furthermore, subjects who come off study for reasons other than PD will be followed for progression, and all patients who come off study will be followed for survival every 4 months for up to 2 years from study start date.

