13.1 Tumor assessment by RECIST v1.1 (primary endpoint)

13.1.1 Definitions for measurable disease and target lesions

Criteria for target lesions

- Lesions that are ≥ 10 mm (long axis) on CT (slice thickness 5 mm or less) orMRI
- Lymph nodes must be ≥ 15 mm (short axis) on CT (slice thickness 5 mm or less) orMRI
- Up to 5 target lesions in total can be reported, and a maximum of 2 lesions perorgan
- Target lesions should be the largest and most reproducible lesions on repeatassessments
- Target lesions should be representative of all involvedorgans

Notes:

- The lymphatic system is considered one organ in RECIST v1.1. Therefore, a maximum of 2 lymph nodes that are classified as target lesions should be reported on the RECIST CRF.
- Lesions that were previously radiated or ablated cannot be target lesions unless there was subsequent radiographic progression at those sites.

Criteria for non-target lesions

- Any lesions that don't meet the criteria for target lesions or are above the reporting limit for target lesions
- All other sites of disease that are <10 mm (long axis) on CT or MRI
- Lymph nodes that are ≥ 10 to <15 mm in the short axis on CT or MRI
- Lesions truly non-measurable such as ascites, leptomeningeal disease, pleural and pericardial effusion, inflammatory breast disease, lymphangitic involvement of skin or lung
- Lesions that are not suitable for repeat measurement, e.g. abutting other structures or likely to coalesce with other lesions
- Multiple non-target lesions in the same organ should be reported as a single non-target lesion, e.g. multiple liver metastases

Note: The lymphatic system is considered one organ in RECIST v1.1. Therefore, multiple lymph nodes that are classified as non-target lesions should be reported as a single non-target lesion on the RECIST CRF.

Measurable disease

- Lesions that can be accurately measured in the longest dimension as ≥ 10 mm by CT scan, ≥ 20 mm by chest X Ray, ≥ 10 mm by caliper on clinical exam. Malignant lymph nodes need to be ≥ 15 mm (short axis) on CT.

Non-measurable disease

- All other lesions that do not fit the criteria for measurable disease. All definitions are outlined in RECIST v1.1 reference.⁶¹

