13.2.1 Similarities and differences between iRECIST and RECIST v1.1

In iRECIST, the definitions are identical to RECIST v1.1 for the following:

- Measurable and non-measurable disease including nodal disease
- Numbers and sites of target lesions
- Calculation of sum of diameters (SoD)
- CR, PR, SD, duration
- Confirmation of CR or PR (for non-randomized trials)
- PD for target and non-target lesions

However, the management of new lesions and determination of progression differ:

- For target lesions, the first PD by RECIST v1.1 is iUPD (immune unconfirmed PD).
- iUPD must be confirmed 4-8 weeks later by imaging.
 - o iCPD (immune confirmed PD) is established if there is a further increase in SoD of target disease from iUPD of at least 5mm.
 - o If there is subsequent iPR, iCR, or iSD (determined by RECIST v1.1 compared to baseline), then the iUPD date is ignored and the status is reset.
 - o If there is no change detected from iUPD, then the timepoint response remains iUPD

- Treatment past iUPD is considered only if the patient is clinically stable.
- iUPD can be assigned multiple times as long as iCPD is not confirmed at the next assessment.
- Assignment of non-target lesions follows similar rules.
- New target lesions are recorded separately and not included in SoD of target lesions identified at baseline; the sum of diameters for the new target lesions is determined.
 - o Appearance of new lesions results in iUPD, which requires confirmation at 4-8 weeks.
 - o iCPD is assigned if, on next imaging, additional new lesions appear, there is an increase in new lesions (at least 5mm), or appearance of new lesions.

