17.0 STATISTICAL CONSIDERATIONS

17.1 Sample size calculation

The primary objective of this study is to evaluate the ORR in patients with advanced HCC treated with cabozantinib and pembrolizumab. This Phase 2 trial will be based on Simon's optimal two-stage design.

The null ORR is assumed to be 20%, which was the ORR (by RECIST v1.1) observed in the sorafenib-naïve group treated with nivolumab in the CheckMate 040 trial.⁸ Early phase data with lenvatinib and pembrolizumab as first-line treatment showed an ORR of 35% in the expansion phase and an ORR of 42% in the overall patient population (DLT evaluation and expansion phase) using mRECIST criteria.³⁸ Therefore, the null hypothesis that the true ORR is 20% will be tested against a one-sided alternative that the assumed-true ORR with the tested combination is 38% by RECIST v1.1. The target assumed-true ORR of 38% is believed to adequately represent the potential activity of cabozantinib and pembrolizumab.

Using Simon's optimal two-stage design, 13 patients will be accrued in the first stage. If there are 2 or fewer patients with response (CR or PR) (an observed rate of 15% or less), the study will be suspended for lack of sufficient efficacy. Otherwise, 16 additional patients will be accrued for a total of 29 patients. The null hypothesis (of an ORR of 20%) will be rejected if 9 or more patients have a tumor response (CR or PR) out of 29 patients (an observed ORR of at least 31%). This design yields a type I error rate of 0.10 and power of 80% when the true ORR is 38%.

An accrual period of 24 months and follow-up period of 12 months are anticipated. More than 29 patients may be screened and/or enrolled depending on screen fails or dropouts before starting treatment.

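### Section 13.1.3 lets a single-scan CR or PR count toward the primary endpoint, while Section 13.2.1 treats confirmation as part of RECIST v1.1 for non-randomized trials such as this one

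*Combined protocol and SAP*

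**What the plan says.** **Operative definition.** Section 13.1.3 says "The best overall response is the best response recorded from the start of the treatment until disease progression/recurrence". Its table combines target, non-target and new lesions and has no confirmation step. Section 13.1.4 starts the duration of response when the measurement criteria are first met.

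**Endpoint and decision rules.** Section 4.1 gives the primary endpoint as "Objective response (complete or partial response) per RECIST v1.1 (by blinded central review"). Section 17.1 sets the stage 1 rule, "If there are 2 or fewer patients with response (CR or PR) (an observed rate of 15% or less), the study will be suspended", and the final rule, under which the null hypothesis "will be rejected if 9 or more patients have a tumor response (CR or PR") out of 29. Neither section mentions confirmation.

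**Text pointing the other way.** Section 13.2.1 lists "Confirmation of CR or PR (for non-randomized trials") among the definitions that are the same in iRECIST and RECIST v1.1. Section 2.0 says "This is a non-randomized Phase 2 trial using the Simon's optimal two-stage design". Section 12.0 refers to "participants who have attained a confirmed CR" in a provision on stopping pembrolizumab. Section 13.1.1 states "All definitions are outlined in RECIST v1.1 reference", but under non-measurable disease. Section 13.0 cites the published criteria for response assessment.

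**After treatment stops.** Section 8.4 places no restriction on therapy in post-treatment follow-up. Section 11.5 requests outside scans every 4 months, if available, for patients who stopped for reasons other than progression, in order to date progression. Later anticancer therapy is collected if available.

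**The concern.** Two readers applying this protocol to the same scans can arrive at different numbers of responders. One follows 13.1.3 and counts a CR or PR seen once. The other follows RECIST v1.1 as 13.2.1 describes it and requires a second scan. Both decision rules are whole-patient counts, so one patient can decide the outcome. Three recorded responses in 13 with one unconfirmed become two, and the trial is suspended. Nine recorded responses in 29 with one unconfirmed become eight, and the null is not rejected.

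Blinded central review limits reader bias. It does not remove scan-to-scan measurement variation or short-lived shrinkage, and it does not say how many scans make a responder. No text gives an interval for confirming a response, says how a response with no later scan counts, or says whether stage 1 waits for pending confirmations.

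A secondary gap is that the 13.1.3 window closes only at progression or recurrence. A patient who stops for toxicity before progression and then starts other therapy is still inside it, and nothing excludes a response first seen on a later outside scan.

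**Working it through.** **Inputs from Section 17.1.** n1 = 13, stop if 2 or fewer responses; 16 more patients, n = 29; reject if 9 or more; null ORR 20%, target ORR 38%.

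**Step 1: the plan's own figures.** The probability of rejecting at true response rate p is

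R(p) = sum over x = 3 to 13 of P(X1 = x) × P(X2 ≥ 9 − x), with X1 ~ Bin(13, p) and X2 ~ Bin(16, p).

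R(0.20) = 0.0999 and R(0.38) = 0.8044. These match the stated type I error of 0.10 and power of 80%, so no design figure is in dispute. Also R(0.30) = 0.4927.

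**Step 2: disagreement between the two readings.** Let r be the recorded (single-scan) ORR and u the share of recorded responses that do not confirm, taken as independent across patients. The confirmed rate is r(1 − u). Confirmed counts never exceed recorded counts at either stage, so the readings can differ in one direction only, and

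P(opposite final conclusions) = R(r) − R(r(1 − u)).

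The documents give no value for u; 5% to 20% is an assumption. All 13 and 29 patients are treated as evaluable.

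| Recorded ORR r | u = 5% | u = 10% | u = 15% | u = 20% |
|---|---|---|---|---|
| 20% | 0.0999 − 0.0771 = 0.023 | 0.0999 − 0.0579 = 0.042 | 0.0999 − 0.0423 = 0.058 | 0.0999 − 0.0299 = 0.070 |
| 30% | 0.4927 − 0.4234 = 0.069 | 0.4927 − 0.3549 = 0.138 | 0.4927 − 0.2891 = 0.204 | 0.4927 − 0.2280 = 0.265 |
| 38% | 0.8044 − 0.7444 = 0.060 | 0.8044 − 0.6744 = 0.130 | 0.8044 − 0.5958 = 0.209 | 0.8044 − 0.5110 = 0.293 |

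**Step 3: stage 1 alone, at r = 30%.** P(X1 ≤ 2) is 0.2025 on recorded responses. On confirmed responses it is 0.2371, 0.2755, 0.3177 and 0.3636 for u = 5, 10, 15 and 20%. The chance of opposite stage 1 decisions is therefore 0.035, 0.073, 0.115 and 0.161.

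**Step 4: error rates, each under a further condition that the documents do not establish.**

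- If 20% is a confirmed rate and unconfirmed responses are counted, type I error is R(0.20/(1 − u)) = 0.128, 0.164, 0.210, 0.268.
- If 38% is an unconfirmed rate and confirmation is required, power is R(0.38(1 − u)) = 0.744, 0.674, 0.596, 0.511.

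These are alternatives and cannot both apply. If the rate and the endpoint are on the same basis, neither applies and the planned 0.10 and 80% stand.

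**The case against.** The strongest reply is that confirmation is already incorporated by reference. The endpoint is per RECIST v1.1, Section 13.0 cites the criteria, 13.2.1 says those criteria include confirmation for trials of this type, and 12.0 speaks of a confirmed CR. On that view 13.1.3 is an abbreviated summary. This has force, and it makes confirmation the more likely intention. It does not settle the matter, because 13.1.3 is a stated counting rule and 13.1.4 dates response from the first qualifying scan. The pointer in 13.1.1 sits under non-measurable disease, and 12.0 concerns treatment and defines nothing. The repeat-imaging intervals given elsewhere are for progression. Whether stage 1 waits for pending confirmations is specific to this trial's design and also needs a rule of its own.

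Three further objections stand and limit the point. First, the size rests on an assumed non-confirming share. Second, Section 17.2 restricts the primary analysis to patients on both drugs concurrently for more than 42 days in the first three cycles, so some early toxicity stoppers would not be counted and the calculation on all 13 and 29 is an approximation. Third, the new-therapy gap needs an unlikely sequence: no response on study, a stop for toxicity without progression, new therapy, an outside scan that is obtained and read, and a first response on it. Those scans are requested in order to date progression, and 8.4 bars other systemic anticancer therapy during study treatment.

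A reader might infer that the trial's type I error is inflated or its power lost. The documents do not support that. Section 17.1 does not say whether the 20% benchmark counts confirmed responses. The 38% is a chosen target, set after mRECIST figures of 35% and 42%, and is not an observed rate. Nor do the documents show that anyone intends to choose the counting rule after seeing the scans; they only leave that open.

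**Conclusion.** The point holds as an inconsistency in the definition of the primary endpoint. Followed literally, 13.1.3 and 17.1 count single-scan responses; RECIST v1.1 as described in 13.2.1 does not. The consequence is a real chance that the same data support opposite conclusions. At an assumed non-confirming share of 5% to 20% that chance is small at a recorded ORR of 20% (at most 0.070), but reaches 0.265 at 30% and 0.293 at 38%. Even at 5% it is 0.069 at a recorded ORR of 30%. These figures are illustrative: they assume independence and full evaluability, but do not depend on how the benchmark was counted.

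A change in type I error or power is conditional on a mismatch of basis that cannot be determined from the documents. The new-therapy gap is secondary, remote and unquantified. The point should be corrected before responses are counted; it does not undermine the sample size or the decision bounds.

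**What to change.** In 4.1, 13.1.3 and 17.1, define a responder as a patient with a centrally read CR or PR, confirmed on a subsequent scan and first recorded before any new anticancer therapy. On treatment, the next scheduled 9-week scan suffices. State the minimum interval, taken from the RECIST v1.1 reference the protocol cites.

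In the primary analysis, count a response with no confirming scan as a non-response, and report the unconfirmed ORR as supportive. Use the same rule for 3 of 13 and 9 of 29. Where the stage 1 decision depends on a pending response, resolve the confirmation first.

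Check whether the 20% benchmark and the 38% target are confirmed rates and state the basis in 17.1. If it differs from the endpoint, restate type I error and power.

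**Cost.** Wording in three sections, no new scheduled scans, and no change to 29 patients or the bounds. Stage 1 may wait up to about 9 weeks when the decision turns on a pending response. At 29/24 = 1.21 patients per month that is about 2.5 patients if accrual pauses. ORR may be slightly lower, because patients who stop for toxicity have only outside scans, requested every 4 months if available, and some responses may never be confirmed. The start date of later therapy would be needed for responders.

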¹²EGD must be done within 6 months prior to study initiation to assess for and treat esophageal and gastric varices.

¹³Alpha fetoprotein (AFP) should be measured at baseline (within 14 days prior to registration). If abnormal at baseline, it should be measured on Day 1 of every 3 cycles starting at cycle 4, and at the treatment discontinuation visit.

¹⁴Disease assessment using multiphasic (four-phase) contrast CT or MRI of abdomen/pelvis, as well as CT chest with or without contrast should be done at baseline (within 28 days prior to registration), and every 9 weeks on treatment (every 3 cycles). If there is disease progression and the patient continues on treatment beyond progression, repeat imaging must be performed 4 weeks later to confirm progression. As clinically indicated, bone scan and contrast imaging of neck may be obtained to monitor disease (see Section 13.3). For the treatment discontinuation visit, the most recent scans are used. For patients who come off study for toxicity, subsequent restaging scans will be requested and assessed at least every 4 months for up to 2 years from study start date to document the date of progression.

¹⁵Archival tumor tissue is acceptable (paraffin-embedded tumor core biopsy or surgical specimen). If archival tissue is not available, baseline core needle biopsy may be performed (if safe and feasible).

¹⁶Pre-treatment Blood will be collected and stored for correlative studies. Research blood will be collected on Cycle 1 Day 1 and Day 8, as well as Cycle 2 Day 1.

¹⁷Informed consent/HIPAA, medical/smoking history, AE/medication assessment, physical exam/ECOG, and assessment of inclusion/exclusion criteria are completed within 28 days prior to registration. Baseline lab investigations are completed within 14 days prior to registration, including pregnancy test for women of child-bearing potential (WOCP) and AFP. Baseline imaging for disease assessment may be obtained within 28 days prior to registration.

¹⁸Cycle 1 day 1 testing need not be repeated if completed within 7 days prior.

¹⁹The treatment discontinuation visit should occur 30 days (+7 days) after the last dose of cabozantinib or pembrolizumab (whichever is latest). Most recent scans are used for the treatment discontinuation visit. Note: if a participant initiates a new anti-cancer therapy within 30 days after the last dose of trial

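### Section 13.1.3 names the smallest on-study measurements as the reference for response, which contradicts the baseline reference for partial response in 13.1.2; a minor wording correction to the primary-endpoint rule

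*Combined protocol and SAP*

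**What the plan says.** Section 4.1 sets the primary endpoint: "Objective response (complete or partial response) per RECIST v1.1 (by blinded central review"). Section 13.0 assigns the reading to a central radiology team.

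The reference for each category is given in several places:

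- **PR, section 13.1.2** (target lesions, sub-numbered 12.1.2.1): "At least a 30% decrease in the sum target lesions, taking as reference the baseline sum diameters".
- **Progressive disease (PD), same section:** "At least a 20% increase in the sum target lesions, taking as reference the smallest sum on study recorded since the treatment started", with an absolute increase of at least 5 mm.
- **SD, same section:** too little shrinkage for PR, "nor sufficient increase to qualify for PD, taking as reference the smallest sum diameters since the treatment started".
- **Best overall response, section 13.1.3:** the best response from the start of treatment until progression or recurrence, "taking as reference the smallest measurements recorded since the treatment started to determine response and progression".
- **iRECIST, section 13.2.1:** the CR, PR and SD definitions are listed as identical to RECIST v1.1, and a response after unconfirmed progression is "determined by RECIST v1.1 compared to baseline".

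The 13.1.3 table takes the target-lesion category as an input. Neither section says which sentence governs if they disagree.

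**The concern.** Response and progression need different references. Shrinkage is counted from where the patient started, and regrowth from the lowest point reached. Section 13.1.2 makes that split for PR and PD. The parenthesis in 13.1.3 removes it by giving the smallest measurement as the reference for both.

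The two references coincide at the first post-baseline scan if baseline is the only earlier measurement. They can separate from the second scan onward. Imaging is "every 9 weeks on treatment (every 3 cycles"), so a patient who stays on treatment will have several such scans. A tumour that shrinks by a moderate amount at each scan can pass -30% from baseline without ever falling 30% below its previous low.

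Best overall response is the natural basis for counting a patient as a responder, and section 17.1 acts on small counts: stop at 2 or fewer of 13, reject the null at 9 or more of 29. An ambiguous reference could therefore become a dispute about a single patient at a decision point.

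**Working it through.** **1. The plan's own figures.** Inputs from section 17.1: null ORR 20%, alternative 38%, 13 patients in stage 1, stop at 2 or fewer responses, 16 more patients, reject at 9 or more of 29. The exact probability of rejecting is

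P(p) = sum over x = 3 to 13 of Bin(x; 13, p) × P[Bin(16, p) ≥ 9 − x].

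- P(0.20) = 0.0999, against a stated 0.10.
- P(0.38) = 0.804, against a stated 80%.

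The design figures reproduce. They take the response rate as given and do not depend on which reference is used.

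**2. The same scans under both references.** The sums below are illustrative, in mm. Under 13.1.2 the change is (current − baseline)/baseline. Under a literal 13.1.3 it is (current − smallest earlier sum)/smallest earlier sum, with baseline counted among the earlier sums. The PR threshold of -30% comes from 13.1.2 in both cases.

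| Sums | Reference: baseline | Reference: smallest earlier sum |
|---|---|---|
| 100, 80, 66 | 66/100 − 1 = -34%: PR | 66/80 − 1 = -17.5%: SD |
| 100, 80, 65, 50 | 50/100 − 1 = -50%: PR | steps of -20%, -18.8%, -23.1%: never PR |
| 100, 65, 60 | -35% at scan 1: PR | -35% at scan 1: PR, so best response is the same |

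In the third row the second scan alone would read -7.7% against the previous low. The best response is still PR from the first scan, because 13.1.3 as worded keeps the best response recorded. CR is a disappearance criterion and PD already uses the smallest sum, so neither moves.

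**3. Which sentence is the outlier.** The PR definition in 13.1.2 and the response comparison in 13.2.1 both use baseline. Section 13.1.4 uses the smallest measurements for duration of response and time to progression, both of which end at progression. Only 13.1.3 names that reference for response in so many words. The SD sentence in 13.1.2 comes close, because its trailing reference can be read as covering the shrinkage half as well as the growth half.

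**4. Sensitivity, under an assumption.** Suppose a share f of true responders were lost, so that the effective ORR is 0.38 × (1 − f).

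| Assumed f | Effective ORR | P(reject) |
|---|---|---|
| 0 | 38% | 0.804 |
| 5% | 36.1% | 0.744 |
| 10% | 34.2% | 0.674 |
| 25% | 28.5% | 0.423 |
| 50% | 19% | 0.077 |

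The documents give no value for f. The table shows how this design behaves at a lower ORR. It does not measure the effect of the parenthesis.

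**The case against.** The strongest reply is that PR has only one working definition. Section 13.1.2 states threshold and reference together. Section 13.1.3 states no threshold, and its table receives target-lesion categories that 13.1.2 has already decided. A 30% fall from the smallest sum is written nowhere; it appears only when the 13.1.2 threshold is joined to the 13.1.3 parenthesis. The endpoint is named as RECIST v1.1 with blinded central review, and 13.2.1 shows that the protocol understands RECIST v1.1 response as a comparison with baseline. An experienced reader would probably use baseline. This stands, and it is why the point is minor. It does not remove the contradiction: the sentence defining best overall response still names a reference for response that 13.1.2 does not use.

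A reader might infer three stronger things that the documents do not support.

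- **False responders as well as missed ones.** Sums of 100, 118, 82 give -18% from baseline (SD) but 82/118 − 1 = -30.5% from the smallest on-treatment sum. This requires excluding baseline from the measurements since treatment started. The missed-responder case here counts baseline, and without it the first scan would have no earlier sum to compare with. The two effects rest on different readings and should not be combined.
- **A power loss caused by this wording.** The lower probabilities above rest on assumed shares with no source, and on readers setting aside the explicit PR definition.
- **That 13.1.2 reserves the smallest sum for PD.** It also attaches it to SD, so a correction confined to 13.1.3 would leave a loose end.

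**Conclusion.** Wrong as written, and a minor wording correction to the rule for the primary endpoint. The conflict between 13.1.3 and 13.1.2 is on the page, and 13.2.1 indicates that baseline is intended for response.

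The part at risk is limited to patients whose shrinkage passes -30% from baseline only after the first scan, and who never fall 30% below an earlier low. This assumes a literal reading of 13.1.3 with baseline counted among the earlier sums, and best response taken from the best single scan. Whether any read would be affected depends on the central-read instructions, which are not among the documents. Misclassification of the ORR is therefore possible but not demonstrated. Sample size, stopping rule, type I error and power all stand.

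**What to change.** In section 13.1.3, replace the parenthesis with: *response is judged against the baseline sum, and progression against the smallest sum recorded on study.*

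In the SD definition in 13.1.2, attach the smallest-sum reference to the PD half only, for example: *shrinkage from the baseline sum too small for PR, and growth from the smallest on-study sum too small for PD.* All of section 13.1 then agrees with itself and with 13.2.1.

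Check that the central-read instructions use the same two references. The cost is two edited sentences in an amendment, with no change to data collection, imaging schedule, sample size or decision rule.
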